### JAEB CENTER FOR HEALTH RESEARCH

0.9	1.05
1.0	1.00

- 1044 The correlation between eyes (inter-eye correlation) for each outcome measure will be estimated
- 1045 during the study and is not known at the time of study design. We assume here a correlation of
- 1046 0.8. This assumption is conservative in that it requires a higher number of participants than lower
- 1047 plausible values of r.

1048 The primary way sample size is evaluated is by considering the precision around the point

1049 estimates for the percent change in the outcome measures over four (4) years. Table 6.1 provides

- 1050 the half width of the 95% confidence interval (CI) for the estimated mean percent change per
- 1051 year for combinations of the standard deviation (SD) of the distribution of percent change and
- 1052 sample size. The larger the SD, the wider the CI, meaning the range of possible true values
- 1053 grows.

# Table 6.1. Sample size versus half width of 95% confidence interval for the mean percent change for varying standard deviation values.

	Effective Sample Size (N of participants)				
	n=11 (10)	n= 22 (20)	n= 33 (30)	n= 44 (40)	n=55 (50)
SD=20%	12%	8%	7%	6%	5%
SD=30%	18%	13%	10%	9%	8%
SD=40%	24%	17%	14%	12%	11%
SD=50%	30%	21%	17%	15%	13%

1056Note: The shaded column corresponds to the sample size deemed feasible based on preliminary patient counts1057and financial constraints. Forty (40) participants from Vision Cohorts 1 and 2 will be followed for1058progression

1058 progression.

## 8.2.2 Sample Size Considerations for Comparing Percent Change from Baseline to four (4) Years within Subgroups of Interest – All Outcomes

1061 Another objective for this natural history study will be to explore the association of risk factors 1062 with progression of various functional outcome variables (objective 3). **Figure 6.1** considers 1063 various expected SDs of the distribution of percent change from baseline to four (4) years per

eye and evaluates the power to detect varying differences in average percent change from

- baseline to four (4) years, comparing subgroups of various equally distributed sizes. If subgroups
- are not equally sized the smallest detectable difference (with the same power) will be larger.
- 1067 Testing will be performed with a Type I ( $\alpha$ ) error rate of 0.05.
- Note: *within* subgroup point estimates and Cis will also be important. Table 6.1 above can be
   applied to potential subgroup sample sizes as well to consider the precision that would be
   observed.

[figure not shown]

Figure 6.1. Power to conclude there is a difference given varying true difference values, population standard
 deviation, and sample size.

1073 For the graphs is Figure 6.1, the y-axis if for the power to conclude that there is a difference

1074 when the true difference in mean percent change is the x-axis value. Each of the four graphs is

1075 for a different total sample size with the number of eyes in each of the two subgroups being

1076 approximately fifty percent (50%). Forty (40) participants from Vision Cohorts 1 and 2 will be 1077 followed.

For example, with an effective sample size of twenty-two (22) and an effective sample size of eleven (11) in each subgroup, to have power of 80% or more, the true difference needs to be

approximately 1.25 SDs (a mean difference of 25% if the SD of the percent change over four (4)

- years 20%). If the effective sample size is thirty-three (33), the true difference needs to be
- approximately 1.0 SD (a mean difference 20% if the SD of the percent change over four (4)
- years is 20%). If the effective sample size is forty-four (44), the true difference needs to be
- approximately 0.86 SDs (a mean difference 17% if the SD of the percent change over four (4)
- 1085 years is 20%). Such mean differences are considered large.

1086 **8.2.3 Sample Size Considerations for Precision of the Estimate of the Correlation** 

# 1087Between Structure-based, Function-based, and Metabolic-based Outcomes and of the1088Correlation Between Eyes

- 1089 The Pearson correlation coefficient (r) can be used to assess the correlation between two
- 1090 different outcome measures. The distribution of r is not symmetric; therefore, CIs for the
- estimated correlation coefficient are not symmetric. A transformation of r ( $z = 0.5 * \ln ((1+r)/1-$
- r)) is used to create a variable that is asymptotically distributed N (0, 1/(sqrt(N-3))) under the
- 1093 null hypothesis that r=0.
- 1094 The intraclass correlation coefficient is used to assess the strength of agreement between eyes.
- 1095 When both eyes have the same mean for the outcome measure, the intraclass correlation
- 1096 coefficient is equal to the standard Pearson correlation coefficient (r). The table below provides 1097 the 95% CI for different estimates of r from the observed data.

# Table 6.2A. 95% Confidence Intervals for an Observed Value of the Correlation between Outcome Measures.

	Effective sample size				
r	n=11	n= 22	n= 33	n= 44	n=55
0.3	(-0.37,0.76)	(-0.14,0.64)	(-0.05,0.58)	(0.00,0.55)	(0.04,0.52)
0.4	(-0.26,0.81)	(-0.03,0.70)	(0.07,0.65)	(0.12,0.62)	(0.15,0.60)
0.5	(-0.14,0.85)	(0.10,0.76)	(0.19,0.72)	(0.24,0.69)	(0.27,0.68)
0.6	(0.00,0.88)	(0.24,0.82)	(0.32,0.78)	(0.37,0.76)	(0.40,0.75)
0.7	(0.17,0.92)	(0.39,0.87)	(0.47,0.84)	(0.51,0.83)	(0.53,0.81)
0.8	(0.38,0.95)	(0.57,0.91)	(0.63,0.90)	(0.66,0.89)	(0.68,0.88)
0.9	(0.65,0.97)	(0.77,0.96)	(0.81,0.95)	(0.82,0.94)	(0.83,0.94)

1100 **Table 6.2B. 95% Confidence Intervals for an Observed Value of the Inter-eye Correlation.** 

	N of patients				
r	n=10	n= 20	n= 30	n= 40	n=50
0.3	(-0.41,0.78)	(-0.16,0.66)	(-0.07,0.60)	(-0.01,0.56)	(0.02,0.53)
0.4	(-0.31,0.82)	(-0.05,0.72)	(0.05,0.66)	(0.10,0.63)	(0.14,0.61)
0.5	(-0.19,0.86)	(0.07,0.77)	(0.17,0.73)	(0.22,0.70)	(0.26,0.68)
0.6	(-0.05,0.89)	(0.21,0.82)	(0.31,0.79)	(0.35,0.77)	(0.39,0.75)
0.7	(0.13,0.92)	(0.37,0.87)	(0.45,0.85)	(0.50,0.83)	(0.52,0.82)
0.8	(0.34,0.95)	(0.55,0.92)	(0.62,0.90)	(0.65,0.89)	(0.67,0.88)
0.9	(0.62,0.98)	(0.76,0.96)	(0.80,0.95)	(0.82,0.95)	(0.83,0.94)

- Note: The shaded column corresponds to the sample size deemed feasible based on preliminary patient counts 1101
- 1102 and financial constraints. Forty (40) participants from Vision Cohorts 1 and 2 will be followed and used for
- 1103 assessing inter-eye correlation of change in outcome measures over time.

#### **8.2.4 Final Sample Size Justification** 1104

- Longitudinal changes in all outcome parameters being collected will be of interest for objectives 1105
- one (1) and three (3). Information on rates of decline using the proposed outcome measures for 1106
- *OAT* variants does not exist. Information on rates of decline for inherited retinal 1107
- degenerations in general is limited. 1108

#### Data to consider for evaluating sample size: 1109

- Valproic Acid Protocol (VPA) Data (phase II multiple sites, randomized, placebo-1110 1111 controlled trial of oral valproic acid for ADRP) [Placebo group N=44; dataset can be accessed at https://public.jaeb.org/ffb/stdy] 1112
  - Percent Change from Baseline to 1 year, Mean (SD):
- 1114

1113

1118

1120

- -0.3% (16%) OD -4.9% (17%) OS
- 1115 1116 **Assumptions made:**
- Expect average annual decline due to *OAT* will be 5% per year or 20% by four (4) years. 1117
- True SD of percent change at four (4) years is like VPA 1-year SD of approximately 20%. 1119

#### If thirty (30) study participants or thirty-three (33) effective eves are recruited: 1121

- The half width of a 95% CI around the point estimate for mean percent change would be 1122 1123 seven (7) %.
- A comparison of two equal-sized subgroups would have about 80% power to conclude 1124 1125 there is a difference if the true difference is 20%.
- For the objective of evaluating the agreement in outcome between eves, a sample size of 1126 thirty (30) participants for Vision Cohorts 1 and 2 will yield a 95% CI of (0.17,0.73) 1127 when the observed r equals 0.5, and (0.62, 0.90) when the observed r equals 0.8. 1128
- For the objective of evaluating the correlation between outcomes, an effective sample 1129 size of thirty-three (33) participants for Vision Cohorts 1 and 2 will have a 95% CI of 1130 (0.19, 0.72) when the observed r equals 0.5, and (0.63, 0.90) when the observed r equals 1131 0.8. 1132
- 1133

#### If forty (40) study participants or forty-four (44) effective eyes are recruited: 1134

- The half width of a 95% CI around the point estimate for mean percent change would be 1135 six (6) %. 1136
- A comparison of two equal-sized subgroups would have about 80% power to conclude 1137 there is a difference if the true difference is 17%. 1138
- For the objective of evaluating the agreement in outcome between eyes, a sample size of 1139 forty (40) participants for Vision Cohorts 1 and 2 will yield a 95% CI of (0.22,0.70) when 1140 the observed r equals 0.5, and (0.65, 0.89) when the observed r equals 0.8. 1141

For the objective of evaluating the correlation between outcomes, an effective sample size of forty-four (44) participants for Vision Cohorts 1 and 2 will yield a 95% CI of (0.24,0.69) when the observed r equals 0.5, and (0.66,0.89) when the observed r equals 0.8.

## 1146 8.3 Data Analysis

1147 The analysis plans below are written with respect to most outcomes of interest. Analyses will 1148 include data on both eyes for each participant, and confidence intervals will be adjusted for 1149 correlation between two (2) eyes of the same participant.

### 1150 8.3.1 Primary Objective Analysis

1151 The primary objectives of the natural history study and brief analysis plan for each are as 1152 follows.

**1.** Natural History 1153 (a) Characterize the natural history of retinal degeneration associated with 1154 disease-causing OAT variants over four (4) years, as measured using 1155 functional, structural, and patient-reported outcome measures. 1156 1157 i. Functional and structural measures: The distribution of each 1158 outcome at each visit will be summarized (including tabulating 1159 categorically, as well as means, SDs, medians, quartiles, ranges; both 1160 the absolute change and percent change will be evaluated, tests 1161 performed multiple times per visit will be analyzed using the average 1162 of all available tests). To determine the average annual rate of 1163 progression in the population for each outcome, a mixed effects model 1164 will be fit using all available outcome data at baseline and all annual 1165 visits. Both the correlation in outcomes over time and the correlation 1166 in outcomes between eyes will be accommodated by the model. 1167 Mixed models adequately accommodate missing values when missing 1168 values are missing at random (MAR). A second method of 1169 accommodating missing values will be through multiple imputation for 1170 the outcome values for all missing time points (including participants 1171 who discontinue follow up prior to forty-eight (48) months). 1172 Secondary analyses using binary definitions of outcome measures will 1173 also be explored in time to event analyses; Kaplan-Meier estimates 1174 with 95% confidence intervals will be calculated. 1175 1176 **PRO measures:** The scoring of each questionnaire will be completed ii. 1177 according to the procedures recommended by the developers of the 1178 questionnaire for each instrument. Baseline scores will be cross 1179 tabulated with categorical (severity of disease) versions of the outcome 1180 measures of interest at baseline. Changes in scores will be cross 1181 tabulated with binary (progression of disease) versions of the outcome 1182 measures of interest at the 24- and 48-month visits. A generalized 1183 linear model adjusted for baseline differences will be explored. 1184

1185	Partially completed questionnaires will be managed using methods
1186	recommended by the developers of the specific questionnaire. When
1187	no questionnaire is completed, we will use statistical methods that
1188	mitigate the impact of missing data, specifically, mixed effects
1189	regression models and multiple imputation for the outcome values for
1190	all missing time points.
1191	
1192	(b) Characterize the natural history of ornithine levels associated with disease-
1193	causing OAT variants in the presence of standard care dietary treatment
1194	regimens over four (4) years.
1195	
1196	i. Longitudinal annual measures of ornithine will be explored by
1197	graphing the values for everyone ("spaghetti" plots) and analyzed to
1198	detect any linear trend in time with mixed effects models.
1190	detect any mical field in time with mixed effects models.
1200	(c) Determine within-patient variability of ornithine levels associated with
1200	disease-causing OAT variants in the presence of standard care dietary
1201	treatment regimens over four (4) years.
1202	
1203	i. The within-person standard deviation of ornithine levels will be
1204	estimated for the group of patients using a mixed effects model.
1205	Models will be based on levels from blood dot tests and from plasma
1206	testing over the four (4) years to determined long -term variability and
1207	on levels from blood dot tests over periods of six (6) months and of
1208	twelve (12) months to determine short-term variability. The coefficient
1209	of repeatability will be calculated to estimate the difference from
1210	baseline that would need to be exceeded to indicate that a treatment
1211	was causing an effect beyond random variability.
1212	2. Metabolic, Structure, and Function Relationships
1213	(a) Evaluate cross-sectional associations at baseline and each annual visit with
1214	scatterplots and Spearman correlation coefficients. Evaluate the association of
1215	changes in each outcome measure with changes the other outcome measures
1216	at each visit with scatter plots and Spearman correlation coefficients. Use
1217	mixed effects regression models to evaluate the association of change in each
1218	outcome measure with changes in each of the other outcome measures. With
1219	so many outcomes and only forty (40) patients, results will be interpreted
1220	cautiously because of both low powers to detect clinically meaningful
1221	associations and elevated Type I error rates due to multiple comparisons.
1222	3. Identify Rapid Progressors
1223	(a) The distribution of each outcome in terms of both absolute change and percent
1224	change from baseline to four (4) years will be summarized (including
1225	tabulating categorically, as well as means, standard deviations, medians,
1226	quartiles), stratified by categorical levels of each potential risk factor of
1227	interest (listed below). Potential risk factors to evaluate include phenotypic
1228	factors including the baseline level of each of the structural and functional
	-

1229	measures and ornithine level, genotype, and adherence to the arginine-
1230	restricted diet as noted below. Univariable regression models of each outcome
1231	measure will be fit for each of the potential risk factors. With so many
1232	potential risk factors and outcomes and only forty (40) patients, results will be
1233	interpreted cautiously because of both low powers to detect clinically
1234	meaningful differences and elevated Type I error rates due to multiple
1235	comparisons.
1236	
1237	i. Phenotypic:
1238	
 
Age of onset of initial vision symptoms
 

1239	
 
Gender
 

1240	Race/ethnicity
1241	
 
Body weight/BMI
 

1242	
 
Lens Status (phakic/pseudophakic/aphakic) and area of
 

1243	subcapsular cataract on red reflex photos
1244	
 
Baseline foveal avascular zone (FAZ) area and macular vessel
 

1245	density on OCTA
1246	
 
Baseline visual acuity
 

1247	
 
Baseline low luminance visual acuity
 

1248	
 
Baseline area of preserved retina on fundus autofluorescence
 

1249	and color photos
1250	
 
Baseline full Hill of Vision (HOV) on static perimetry
 

1251	
 
Baseline mean sensitivity on static perimetry
 

1252	
 
Baseline mean retinal sensitivity on microperimetry
 

1253	
 
Baseline full-field stimulus (FST) levels
 

1254	
 
Baseline ERG amplitude and timing
 

1255	
 
Baseline ellipsoid zone (EZ) area on OCT
 

1256	
 
Baseline ornithine level
 

1257	
1258	ii. Genotypic
1259	
 
Characterizations of the OAT variants
 

1260	
1261	iii. Environmental Factors
1262	
 
Adherence to arginine-restricted diet
 

1263	
 
Smoking
 

1264	

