558 559 560 561 562 563	detailed in and certif	wing procedures will be performed at the Baseline Visit. The testing procedures are in the GYROS Clinical Site Manual of Procedures . An overview of the equipment fication requirements for all testing is in Chapter 5.1: Study Procedure nents . All ocular testing will be performed in each eye, OD first and then OS. Baseline es will last approximately seven $(7) - eight (8)$ hours. Baseline procedures will span 10) days.
564	3.3.1	Baseline Data Collection and Testing Cohorts 1 & 2
565	1.	Medical updates to include:
566		• New or changed adverse events (AEs)
567		New ocular procedures
568		New or changed medications
569		• Request medical records and laboratory records if applicable.
570	2.	Patient Reported Outcomes
571		
 
Adults: PROMIS®-29, MRDQ, ViSIO-PRO
 

572		
 
Adolescents: LPV-FVQ II, ViSIO-PRO
 

573		Children: LPV-FVQ II
574 575 576		• The PROs may be completed in person or remotely (phone or other remote methods) any time within six (6) months of the Baseline Visit (not required to be the same day as the rest of the Baseline Visit).
577	3.	Skin biopsy (3mm punch skin biopsy)
578		• Ship to Johns Hopkins University Department of Genetic Medicine Research Lab
579	4.	Spectral Domain Optical Coherence Tomography (SD-OCT)
580		Volume Scan
581		Vertical and Horizontal Scan
582	5.	Axial Length and Corneal Curvature Measurements
583	6.	Fundus Autofluorescence
584	7.	Widefield color photo

585	8. Optical coherence tomography angiography (OCTA)
586	• Ancillary test; may be waived with approval from the Coordinating Center
587	9. Red reflex photo
588	10. Full field Stimulus Threshold (FST)
589	11. Static perimetry
590 591	• Two (2) tests will be performed. The clinical site will compare the certified technician determined mean sensitivity from test one (1) versus test two (2).
592 593 594 595	
 
(a) If the absolute value of the difference between the two tests is ≤ 2.4 dB, then the participant passes static perimetry reliability criteria. A third test is not needed.
 

596 597 598	(b) If the absolute value of the difference between the two tests is > 2.4 dB, then the participant does not pass static perimetry reliability criteria. A third test will be required .
599	12. Fundus guided microperimetry

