# 1032 8.2.1 Sample Size Considerations for Evaluating Percent Change from Baseline to four 1033 (4) Years – All Outcomes

1034 Longitudinal changes on all outcome parameters being collected will be examined with the

1035 change in preserved retina being of particular interest. Change from baseline to four (4) years

1036 will be evaluated for sample size purposes, although statistical analyses will include the data

1037 from each annual visit. The power and sample size calculations below may be used to consider

1038 percent change on any outcome measure from baseline to four (4) years.

1039 Both eyes of a participant will be assessed for the main outcomes of interest. Thus, if there are N

1040 participants, 2N eyes will be available for analysis. However, outcome measures from two (2)

1041 eyes of a person are typically strongly correlated ( $r \ge 0.5$ ). The contribution of information from

1042 the two (2) eyes in this case is (2/(1+r)) instead of two (2). Values for the multiplier to the

1043 number of participants to obtain an effective sample size are given below:

r	Effective N
0.0	2.00
0.1	1.82
0.2	1.67
0.3	1.54
0.4	1.43
0.5	1.33
0.6	1.25
0.7	1.18
0.8	1.11

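### Percent change is planned for perimetry mean sensitivity, which is in decibels, so low-baseline eyes can look like rapid progressors when their dB loss is the same

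*Protocol*

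**What the plan says.** - **Analysis, objective 1.** Protocol 8.3.1 item 1(a)i, on functional and structural measures, states that both "the absolute change and percent change will be evaluated" for each outcome. The annual rate of progression comes from a mixed effects model, with no percent scale mentioned.
- **Analysis, objective 3.** Item 3(a) summarises, by level of each risk factor, "The distribution of each outcome in terms of both absolute change and percent" change from baseline to four years. The listed risk factors include baseline mean sensitivity on static perimetry and on microperimetry.
- **Scope.** Section 8.3 opens with "The analysis plans below are written with respect to most outcomes of interest". It does not say which outcomes fall outside.
- **Sizing.** Section 8.2.1 says its calculations may be used for "percent change on any outcome measure from baseline to four (4) years". Section 8.2.2 sets power for subgroup comparisons of mean percent change at a Type I error of 0.05. Section 8.2.4 assumes a 20% decline and a 20% SD at four years. The SD comes from a one-year placebo group whose outcome measure is not named.
- **Units.** Section 3.3.1 item 11 judges agreement of repeat static perimetry in absolute dB: "If the absolute value of the difference between the two tests is ≤ 2.4 dB", no third test is needed. Item 12 uses a 50% relative rule for microperimetry, with an absolute alternative of 0.5 dB.

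No rule confines percent change to certain outcomes or sets a minimum baseline.

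**The concern.** Percent change is meaningful when zero means none of the quantity, as with an area. A decibel value is already a logarithm, and its zero depends on the instrument's reference level. (This is general measurement knowledge; the protocol does not discuss it.) Dividing a dB difference by a dB baseline therefore gives a number that depends on where the eye started and where the instrument put its zero, as well as on how much sensitivity was lost.

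Two uses are exposed. First, the mean and SD of percent change for dB outcomes depend on the baseline mix, so one planning SD cannot be carried across outcomes. Second, objective 3 looks for rapid progressors and lists baseline sensitivity as a candidate risk factor. On the percent scale that factor is also the denominator of the outcome, which builds in an association. The Protocol Summary says the study should show which measures are most sensitive to change and inform eligibility for a future trial, so a scale artefact here could be carried forward.

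**Working it through.** **1. The plan's own figures reproduce.** Effective N = 40 × 2/(1 + 0.8) = 44.4, used as 44. Half-width = 1.96 × 20%/√44 = 5.91%, stated as 6%. Power for a 0.86 SD difference with 22 per group, two-sided 0.05, is 79.6% by the t test, stated as about 80%. The arithmetic is sound; the question is the scale.

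**2. Equal losses, unequal percentages.** A 2 dB loss multiplies linear sensitivity by 10^(-0.2) = 0.631, a 37% fall from any baseline. As a percentage of the dB value (illustrative baselines):

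| Baseline | 2 dB loss | Same loss, zero moved by 10 dB |
|---|---|---|
| 20 dB | -2/20 = -10% | -2/30 = -7% |
| 10 dB | -2/10 = -20% | -2/20 = -10% |
| 5 dB | -2/5 = -40% | -2/15 = -13% |
| 4 dB | -2/4 = -50% | -2/14 = -14% |

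The protocol's own 2.4 dB retest limit is 12% of 20 dB and 20% of 12 dB. The second equals the whole four-year decline assumed in 8.2.4.

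**3. Dependence on the baseline mix.** Assume a change of -2 dB (SD 1.5 dB) in all eyes, follow-up floored at 0 dB, and uniform baselines. Half-width is 1.96 × SD/√44.

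| Baselines | Mean percent change (SD) | 95% half-width, n = 44 |
|---|---|---|
| 15-25 dB | -10% (8%) | about 2% |
| 5-25 dB | -16% (15%) | about 5% |
| 2-25 dB | -21% (24%) | about 7% |
| 1-25 dB | -23% (27%) | about 8% |

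The loss in dB is essentially the same in every row.

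**4. Objective 3.** Give every eye the same expected loss of 2 dB and split at the middle of a 5-25 dB range. For uniform baselines from a to b, the mean of 1/baseline is ln(b/a)/(b - a).

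- Low half, 5-15 dB: -200 × ln(3)/10 = -22.0%.
- High half, 15-25 dB: -200 × ln(5/3)/10 = -10.2%.

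This gap of about 12 percentage points arises with no difference in dB loss. Simulating 22 against 22 independent eyes, two-sided 0.05, the share of samples falsely showing faster percent progression in low-baseline eyes was:

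| Assumed baselines | Percent change | Absolute change |
|---|---|---|
| 10-25 dB | 38% | about 5% |
| 5-25 dB | 70% | about 5% |
| 2-25 dB | 84% | about 5% |

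A rerun reproduces these rates with an assumed SD of change of about 1.6 dB. For 5-25 dB, the rate is 97%, 76% and 53% at SDs of 1.0, 1.5 and 2.0 dB. Baseline is taken as error-free, so regression to the mean is left out.

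**The case against.** Much of the other side stands.

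- **An interpretable analysis exists.** Absolute change is planned beside percent change throughout, and the mixed-model rate is not tied to percent. Medians and quartiles are also reported, and they are less exposed to extreme ratios than means and SDs.
- **A reader might infer that the whole sample size rests on percent change.** It does not. Section 8.2.1 says "The primary way sample size is evaluated is by considering the precision around the point" estimates of percent change, but 8.2.3 sizes correlations separately ("The Pearson correlation coefficient (r) can be used to assess the correlation between two" outcome measures), and Tables 6.2A and 6.2B are untouched. The note to Table 6.1 describes the chosen column as the "sample size deemed feasible based on preliminary patient" counts and finances.
- **A reader might extend the point to every functional outcome, letter scores or questionnaires.** Section 8.3 claims only most outcomes. Questionnaires have their own plan in item 1(a)ii, without percent change. The argument here rests on the dB unit, which the protocol shows only for the two mean sensitivities, not for the Hill of Vision measure or the full-field stimulus threshold.
- **The key measures are areas.** Preserved retina is of particular interest in 8.2.1 and has a true zero.
- **Table 6.1 spans SDs of 20% to 50%.** A reader can pick a larger SD, although 8.2.4 carries only 20% forward.
- **Low dB baselines are not documented.** The protocol gives no sensitivity distribution, Vision Cohort 3 has no perimetry, and about 25 of the 40 participants in Vision Cohorts 1 and 2 are in Cohort 1. The 0.5 dB alternative for microperimetry can matter only when the two-test average is below 1 dB, since 0.5/1 = 50%. That suggests such eyes were foreseen, but the protocol gives no reason for the rule.

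The objection that outcome-specific scales belong in the SAP is weaker: the protocol does not leave the scale open, but names percent change for each outcome. The caution about multiple comparisons in item 3 does not cover this artefact either, because it is systematic and runs in one direction.

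**Conclusion.** The point holds for mean sensitivity on static perimetry and microperimetry, in the percent-change summaries of 8.3.1 items 1(a)i and 3 and in the offer of the 8.2.1 precision to any outcome. That equal dB losses give unequal percentages is arithmetic and needs no assumption about the data. The size of the false signal in objective 3 does: about 70% against 5% at baselines of 5 to 25 dB, 38% at 10 to 25 dB and 84% at 2 to 25 dB, and it also moves with the assumed SD of change. If all enrolled eyes had high and similar baselines, the distortion would be small.

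A reader might infer that the study lacks a valid perimetry analysis or that 40 participants is no longer justified. Neither follows: absolute change and the mixed model are planned, and the area outcomes and correlation precision are unaffected. Nor should a figure be put on percent-change noise at baselines near zero. A ratio with a normal denominator has no finite variance, and simulated values there are unstable.

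The change is worth making because the percent summary can mislead in the analysis meant to identify rapid progressors.

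**What to change.** - **8.3.1 items 1(a)i and 3:** limit percent change to outcomes with a true zero, such as preserved-retina, lesion and ellipsoid zone areas, in eyes above a stated baseline floor. Use absolute change alone for mean sensitivity in dB.
- **8.2.1 and 8.2.4:** replace the reference to any outcome measure with those outcomes, and name the outcome to which the 20% SD refers.

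The cost is a few sentences and the loss of the percent column for dB outcomes. Sample size, visits and data collection do not change.
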